1.2 Primary Objectives

- 1.2.1 To measure the effect of high doses of radiation on trabecular bone mineral density (Tb. TBD) in the adult sacrum using the quantitative computer tomography technique (QCT) in patients undergoing treatment with combination surgery and adjuvant radiotherapy, or radiation alone.

CONFIDENTIAL

This document is confidential. Do not disclose or use except as authorized.

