Quantitative computer tomography analysis (QCT) is a high resolution imaging technique that can detect changes in bone mineralization density and trabecular bone density [20, 33]. Figure 5 (E) shows the difference between two bone types. Cortical bone is thick and solid, and provides the weight-bearing strength of bone. Trabecular bone is porous, and has a woven-like structure. Radiation causes sclerosis of the trabecular bone, rendering it solid and dense, like cortical bone. Despite this increase in density, irradiated bone becomes brittle and prone to fractures. Traditional method of measuring bone density by dual-energy X-ray absorptiometry (DEXA) measures an average density of cortical and trabecular bone. It cannot differentiate between normal bone and fragile, irradiated bone affected by sclerosis. QCT can measure the density of trabecular bone directly. Figure 5(A-C) shows the axial, coronal and sagittal scans of the lumbar vertebral body by QCT. A three-dimensional reconstruction of a slice through the vertebral body allows determination of the architecture of the trabecular bone, as illustrated in Figure 5(D).

Figure 5: Determination of Bone Structure in the Adult Spine by Quantitative CT (QCT)

CONFIDENTIAL

This document is confidential. Do not disclose or use except as authorized.

[figure not shown]
Calculation of the bone mineral density and trabecular bone density by QCT in the adult spine. A. Axial cut through the body of the L1 vertebra showing the difference in density of the cortical bone (bright white) and trabecular bone (gray). B. Coronal and C. Sagittal reconstructions of the same L1 vertebra show the woven porous structure of the trabecular bone. D. A rendered, sagittal slice of 10 mm thickness shows the trabecular structure in 3-D. E. Illustrates the difference in the structure of the cortical and the trabecular bone in the lumbar vertebral body.

Bone density can be calculated from the radiopacity of the bone expressed in Hounsfield units, averaged over a small region of interest (ROIs) as shown in Figure 6. In the lumbosacral spine, ROIs are drawn through the anterior aspect of the L4, the sacral alae, and midline of S1, avoiding any areas of abnormal anatomy or sclerosis due to fractures or degenerative changes. The Hounsfield unit values are then entered into software to calculate values for the trabecular bone mineral density (Tb. BMD) in the region of interest.

Figure 6: Definition of ROI in the Lumbar Spine

CONFIDENTIAL

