3. PARTICIPANT SELECTION

3.1 Eligibility Criteria

All laboratory tests that are a part of the eligibility criteria must be completed within 14 days prior to the date of registration. Diagnostic tests that are a part of the eligibility criteria must be performed within 30 days of the date of registration. Participants must meet the following criteria on screening examination to be eligible to participate in the study:

- 3.1.1 Study participants must have histologically confirmed primary malignant bone tumor in the sacrum for which surgery and radiation or radiation alone are planned.

CONFIDENTIAL

This document is confidential. Do not disclose or use except as authorized.

- 3.1.2 Age 18 years or older. In children under the age of 8, tetracycline derivatives have been reported to stain tooth enamel yellow color. These considerations lead us to exclude young persons under the age of 18 from the study.
- 3.1.3 Participants in the surgical arm must have normal organ and marrow function as defined below:
- Total bilirubin within normal institutional limits
 - AST (SGOT)/ALT (SGPT) < 2.5 X institutional upper limit of normal
 - Creatinine within normal institutional limits or creatinine clearance > 60 mL/min/1.73 m² for subjects with creatinine levels about institutional normal limit
- 3.1.4 The effects of tetracyclines and radiation used in computer tomography on the developing human fetus are known to be detrimental. For this reason, women of child-bearing potential and men must agree to use adequate contraception (hormonal or barrier method of birth control; abstinence) prior to study entry and until after the last study related computer tomography scan . Should a woman become pregnant or suspect she is pregnant while participating in this study, she should inform her treating physician immediately.
- 3.1.5 Ability to understand and willingness to sign a written informed consent.

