5. TREATMENT PLAN

CONFIDENTIAL

This document is confidential. Do not disclose or use except as authorized.

Study participants will receive treatment as determined by their treating physicians at the Massachusetts General Hospital for Malignant Bone Tumors of the Sacrum. This may be radiation alone or pre-operative radiation therapy followed by surgery. The treatment plan including MRI and CT imaging is determined by the clinical situation and not by the study. Patients planned for surgery typically receive pre-operative MRI of their pelvis and/or sacrum. In addition, patients often receive a pelvic or sacral computed tomographic image. A CT of the chest is performed to evaluate for pulmonary metastasis. Figure 9 outlines the current standard radiation treatment options. Study participants may also receive radiation therapy as part of another clinical trial. For surgical candidates, the standard treatment includes pre-operative radiation of 50.4 Gy, followed by a recovery period of approximately 4 to 5 weeks. Surgery involves removing the malignant tumor in the sacrum in one piece, preferably with a cuff of normal tissue around the tumor. After approximately 6 weeks of recovery, to allow the surgical incision to heal, the patient is treated with another 19.8 Gy up to 27 Gy of radiation postoperatively depending on the final margin status (higher for gross residual disease), as outlined in Figure 9(A). If the wound is not healed or there is another medical reason to delay adjuvant radiation, then radiation may begin later. The patients are typically followed every 3 months with an MRI of the pelvis/sacrum to evaluate for a local recurrence. A CT scan is often ordered if there is a concern for a fracture. In addition, patients typically receive a chest x-ray at 3 months and 9 months after surgery. A chest CT is ordered at 6 months and 12 months after surgery. The same protocol is used during the second year of follow up. Non-surgical candidates receive 72 up to 77.4 Gy of radiation depending on the histology (72 Gy for osteosarcoma and chondrosarcoma and 77.4 Gy for chordoma) as outlined in Figure 9 (B).

Figure 9: Radiation Treatment Flowchart

CONFIDENTIAL

This document is confidential. Do not disclose or use except as authorized.

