Will perform a volumetric dual energy CT of L1, L2, and S1 using a second-generation dual-source 128-row multi-detector CT scanner (Somatom Definition Flash; Siemens Medical Solutions, Forchheim, Germany). Subjects will be positioned on a quantitative CTPRO calibration phantom (Mindways Software). Helical scans will be performed at 80 and 140 kV by using 210 and 80 mAs, respectively. Other scanning parameters included 1-second gantry rotation time, 0.9:1 pitch, and 64 x 0.6-mm detector configuration with double z-sampling. The images will be reconstructed at 2-mm section thickness and 2-mm section interval by using the I31f reconstruction kernel with a sinogram-affirmed iterative reconstruction (SAFIRE; Siemens Healthcare) setting of 2. The effective dose for each DECT scan is about 2 mSv. For 2 scans, the total effective dose is about 4 mSv which is about the annual background radiation dose.

6.2 **Toxicity Management**

6.2.1 *Management of Tetracycline Toxicity*

Renal / Hepatic Impairment: Tetracycline will not be administered to patients with pre-existing renal or hepatic impairment.

Photosensitivity: Patients will be advised to use skin protection while taking tetracycline. In addition, patients will be advised against prolonged exposure to sunlight and use of tanning equipment. If skin erythema occurs, patients will be advised to discontinue taking the drug and contact the study team.

Superinfection: Patients will be informed of this risk, and will be closely monitored for any GI symptoms. Patients will be advised to discontinue taking the drug and contact their primary care provider and the study team, if any symptoms of infection occur.

Pseudotumor: Patients will be advised to discontinue taking the drug and contact the study team if headache, photophobia, gait disturbances, or any other neurological deficits occur.

Special populations: pregnant and lactating women and children will be excluded from the study due to the concerns related to tetracycline use in these populations (outlined in Section 6.1.1 Adverse Effects of Tetracycline 6.1.2).

CONFIDENTIAL

This document is confidential. Do not disclose or use except as authorized.

6.2.2 *Management of Demeclocycline Toxicity*

Diabetes Insipidus: Patients will be advised to discontinue taking demeclocycline and contact their PCP and the study team, if they experience excessive thirst, urination, headache, dizziness, nausea/vomiting, or any other concerning symptoms.

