8. CORRELATIVE/SPECIAL STUDIES

8.1 **Pharmacokinetic Studies**

N/A

8.2 **Pharmacodynamic Studies**

N/A

8.3 **Special Studies**

8.3.1 *Blood Draws*

We will follow the trends in serological markers over a 6 month period beginning prior to the first dose or radiation received by the patient. The study Schema outlines specific time points when we plan to draw

CONFIDENTIAL

This document is confidential. Do not disclose or use except as authorized.

the blood samples. After all studies have been performed we will label the samples with a code. The key to the code will connect the sample with the subjects health information. The key to the code will be kept in a password protected computer of the principal investigator. Samples will be stored at the BioBank and Research Laboratory Services for the Maine Medical Center Research Institute.

Figure 10

What is measured:

- N-Telopeptide (NTX)
- Serum tartrate-resistant acid phosphatase 5b (TRAP5b)
- Osteocalcin (OC)
- Type 1 procollagen N-terminal (P1NP).
- PTH
- Calcium as part of a standard metabolic panel
- Phosphate

8.3.2 *Quantitative CT Scans*

Patients in both arms of the study will undergo two QCT scans. First QCT will be done at Day 1, prior to initiation of radiation treatment. Patients in the Non-Surgical Arm will undergo a second QCT at six months after their first radiation treatment. In contrast, patients in the Surgical Arm will undergo their second QCT immediately prior to surgery, 10 weeks after the first scan. Once the spinal instrumentation is introduced during the surgery, it renders the analysis impossible due to artifact. Scans will be performed by the MGH Musculoskeletal Imaging Research Core (MIRC) under the direction of [name] (Radiology). We will use the QCT Pro protocol, detailed in Section 6.1.3 – Radiation Exposure Risks. Volumetric QCT of L1, L2 and S1 vertebrae will be obtained. Images will be saved in standard DICOM format and transferred to a PACS workstation for analysis.

What is measured:

- Trabecular bone mineral density (Tb. BMD)

8.3.3 *Bone Biopsies*

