Bone biopsies will be performed on patients enrolled in the Surgical Arm of the study. Each patient will undergo two biopsies. At the time of each biopsy we plan to collect two bone samples. Figure 10 shows the location of the planned biopsy sites. The first biopsy (the control) will be taken from the iliac wing of the pelvis. This area lies outside of the radiated field, and will serve as a normal bone control. The second biopsy will be taken from the irradiated part of the sacrum. Bone biopsies will be evaluated for the end points of dynamic histomorphometry, and possible radiation-induced woven bone and bone mineralization abnormalities. Micro-CT will be performed on half of the bone samples prior to embedding to evaluate 3D trabecular microstructure. Biopsies that will be used for dynamic histomorphometry will be stored in 10% buffered formalin at room temperature in a dark space. We will send the biopsies to [name] at Columbia University for analysis. Transfers will be done in batches using FedEx. After all studies have been performed we will label the biopsies with a code. The key to the code will connect the biopsy with the subjects health information. The key to the code will be kept in a password protected computer of the principal investigator. Biopsies will be stored either at room

[figure not shown]
CONFIDENTIAL

This document is confidential. Do not disclose or use except as authorized.

temperature (embedded specimen) or frozen (fresh specimen) at the Endocrine Unit Research Laboratory of the Massachusetts General Hospital.

Figure 10 shows the location of two biopsy sites.

Figure 10: Location of the Planned Bone Biopsy Sites.

Biopsies will be done at the time of the scheduled tumor surgery. Sacral tumors are removed in stages. The first stage is done via anterior exposure, allowing access to the iliac crest. We will collect these samples first. Using a 7,5mm Rochester trephine two bone samples will be removed from the superior apex of the iliac wing in the midline (as defined as a point midway between the anterior superior and posterior superior iliac crests). In most cases, the biopsy site will be accessible through the incision made for the anterior approach. However, in those rare cases when the biopsy site is not accessible via the incision made as part of the standard of care, then a separate small incision (at most 3 cm long) will have to be made.

[figure not shown]

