The second stage is done via posterior approach, providing access to the sacrum. We will collect the second biopsy samples during the second stage procedure. Using the same 7,5mm Rochester trephine, two bone samples will be removed from bone within one centimeter of the resection margin. To avoid unnecessary damage to healthy bone, we will attempt to collect the bone samples from the part of sacrum removed in surgery. After the tumor has been resected, it is normally brought to surgical pathology by the surgeon. There the specimen is examined by the pathologist. If there is enough normal bone remaining on the resected specimen, and the pathologist feels that using the normal bone will not interfere with his

CONFIDENTIAL

This document is confidential. Do not disclose or use except as authorized.

ability to assess the margin of resection, then the biopsy will be obtained from the surgical specimen rather than from bone remaining on the sacrum still attached to the patient's spine. Figure 11 illustrates the two possible sites of the sacral biopsy.

Figure 11: Location of Sacral Biopsy Site

Sacral Biopsy. This sagittal MRI image of the sacrum shows a large tumor at the caudal end. The entire sacrum was irradiated in this patient; the extent of the radiation field is approximated by the orange outline. During surgery, an axial cut through the middle of the sacrum was made to remove the tumor with negative margins. The portion of the sacrum removed is outlined in purple. For the purposes of our study, we would always try to take the bone samples from the portion of the sacrum to be discarded (A). In those cases when the fragment removed doesn't have enough healthy tissue for a biopsy, the samples will be collected from the portion of the sacrum that remains attached to the patient's spine (B). The approximate location of the biopsy site is marked with a trephine in A and B.

8.3.4 *Undecalcified Histology*

One control and one experimental sample from the biopsies will be embedded in plastic resin (MMA/dibutylphthalate) then split in half using a fine handsaw (0.3mm kerf). So as to not alter the mechanical properties of bone, one half will be scanned by micro-CT then processed for thin section histology. The other half will be sectioned at 1 mm intervals for quantitative back scatter electron imaging followed by nano indentation.

8.3.5 *Immunohistochemistry*

CONFIDENTIAL

This document is confidential. Do not disclose or use except as authorized.

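### QCT levels are fixed without reference to the radiation field and dose at the measured bone is never recorded, so a null result could not be told apart from low dose at the region read

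*Combined protocol and SAP*

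**What the plan says.** The primary objective (section 1.2) is the effect of high-dose radiation on "trabecular bone mineral density (Tb. TBD) in the adult sacrum using the quantitative computer tomography technique (QCT"). Three other places describe what is measured:

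- Section 8.3.2: "Volumetric QCT of L1, L2 and S1 vertebrae will be obtained". Section 6.1.3 agrees: "Will perform a volumetric dual energy CT of L1, L2, and S1".
- Section 2.4.2 gives different regions: "ROIs are drawn through the anterior aspect of the L4, the sacral alae, and midline of S1". They are placed to avoid abnormal anatomy and sclerosis, with no reference to the treated volume.
- Section 14.1.1 defines the primary endpoint as the change on QCT of the lumbar spine.

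Exposure is set outside the study. Section 3.1.1 admits any "histologically confirmed primary malignant bone tumor in the sacrum for which surgery and radiation or radiation alone are planned", with no restriction on sacral level. Section 5 leaves treatment to the treating physicians and adds: "Study participants may also receive radiation therapy as part of another clinical trial".

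Field coverage is mentioned only in section 8.3.3. Of the iliac biopsy site it says: "This area lies outside of the radiated field, and will serve as a normal bone control". The second biopsy is to come from the irradiated part of the sacrum. The Figure 11 legend says: "The entire sacrum was irradiated in this patient; the extent of the radiation field is approximated by the orange outline".

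Sections 14.2 to 14.4 name treatment type as the only stratum. They propose a Cox stratified model without listing its factors, and rank correlations with the exploratory variables. Dose and field appear in none of these.

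**The concern.** A study of what radiation does to bone needs to know how much radiation the measured bone received. Here the only exposure information is the prescribed course. Tumor level varies, the field is chosen clinically, and the scanned levels are the same for everyone. S1, at the top of the sacrum, is the only sacral level that section 8.3.2 scans. The wording on the irradiated part of the sacrum allows for partial coverage.

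If a patient's sacral region of interest received little dose, that patient would contribute a change near zero to an average labelled as the radiation effect. Without dose at the region, the trial could not separate two explanations of a null: radiation does not change sacral density, or the bone that was read was not heavily irradiated. The same gap affects the comparison of iliac crest with sacrum in section 14.2, which relies on the iliac site being unirradiated in each patient.

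Prescribed dose at the second scan also differs by arm. Surgical patients are rescanned before surgery, after the 50.4 Gy pre-operative course. Non-surgical patients are rescanned after a course of 72 to 77.4 Gy. The analysis does not use this difference either.

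**Working it through.** **Inputs (section 14.2).** Mean change 10 mg/mL; SD of the change 15 (printed as mg/dL, read as mg/mL); alpha 0.05, sidedness not stated; n = 30, 20 and 10.

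**Step 1: reproduce the plan's power.** Take a paired t-test on the within-patient change, two-sided, with df = n − 1 and noncentrality (10/15)√n.

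| n | noncentrality | computed power | stated power |
|---|---|---|---|
| 30 | 3.65 | 0.9416 | 0.942 |
| 20 | 2.98 | 0.8073 | 0.807 |
| 10 | 2.11 | 0.4692 | 0.469 |

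The plan's figures are correct for a mean change of 10 mg/mL at the measured bone.

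**Step 2: allow for low dose at that bone.** Assume a fraction f of patients has low dose at the region read and shows a fraction r of the full effect, while the rest change by 10. The documents give neither f nor r.

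- Mean = 10 × [1 − f(1 − r)]
- Variance = 15² + f(1 − f) × [10(1 − r)]²

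Example, f = 0.1 and r = 0: mean = 10 × 0.9 = 9; variance = 225 + 0.09 × 100 = 234; SD = 15.30.

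Example, f = 0.1 and r = 0.5: mean = 10 × 0.95 = 9.5; variance = 225 + 0.09 × 25 = 227.25; SD = 15.07.

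| f | r | mean | SD | power, n = 20 | power, n = 10 |
|---|---|---|---|---|---|
| 0 | – | 10 | 15.00 | 0.807 | 0.469 |
| 10% | 0 | 9 | 15.30 | 0.704 | 0.383 |
| 20% | 0 | 8 | 15.52 | 0.590 | 0.308 |
| 10% | 0.5 | 9.5 | 15.07 | 0.762 | 0.429 |
| 20% | 0.5 | 9 | 15.13 | 0.713 | 0.390 |

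Simulation with 200,000 runs per case agreed within 0.004. At n = 20, the two values of f correspond to 2 and 4 patients.

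**Step 3: the choice of region matters too.** The plan does not say how levels combine into one primary value. Suppose, purely for illustration, that L1, L2 and S1 were averaged and the lumbar levels did not change. The mean change is then 10/3 = 3.33. Power at n = 20 is 0.157 with SD 15, or 0.373 with SD 15/√3 = 8.66 (independent changes at the three levels). Naming the primary region therefore comes before any question about dose at S1.

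**Step 4: cost of restricting the primary set by dose.** With mean change 10 and SD 15 in those kept, 18, 16 or 12 of 20 patients give power 0.760, 0.703 or 0.558. Exclusion recovers part of the loss at best, and does so at the price of a cut-off for which the documents offer no basis.

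**The case against.** The strongest objection is that nobody has shown the problem occurs. The only patient whose field is described had a large tumor at the caudal end, which is where one would most expect S1 to be spared, and the whole sacrum was in the field. If that is usual practice, f is zero and the stated power stands. One case sets no rule, but it is the only evidence in the documents and it points away from dilution.

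A reader might infer that patients with S1 out of field are being counted as irradiated and are diluting the result. The documents do not support that as fact. Nor do they support saying that the analysis treats every S1 value as irradiated: S1 is never named as the primary value, section 14.1.1 says lumbar spine, and section 2.4.2 reads L4, the alae and S1.

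On the biopsies, section 8.3.3 does state that the iliac site is outside the field and that the sacral sample comes from irradiated bone. Nothing contradicts this; what is missing is a check in each patient.

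The power losses depend on assumed values, and section 14.2 can be read as setting 10 mg/mL for the study population as a whole, variable coverage included. This is also a pilot, meant in part to supply numbers for later studies. These points limit the size of the concern. They do not answer the gap itself: no section records or uses dose at the measured bone.

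**Conclusion.** The concern holds as a conditional risk to interpretation. It is established that the scanned and read levels are set without reference to the field, that the sections disagree on which levels they are, and that delivered dose at the measured bone is neither recorded nor analysed. It follows that a null could not be distinguished from low dose at the region read.

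It is not established that any patient has low dose there. The size is therefore an illustration that rests on assumed f and r and on the plan's own mean and SD: at n = 20, power of 0.704 to 0.762 if one patient in ten is affected, and 0.590 to 0.713 if one in five is. At f = 0 there is no loss. A reader might go on to infer that the primary analysis should be confined to patients above a dose threshold. The documents do not support that step, because they give no basis for a threshold and exclusion itself costs power.

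**What to change.** 1. Reconcile sections 1.2, 2.4.2, 6.1.3, 8.3.2 and 14.1.1 so that one sacral region is the primary site and the same levels are scanned, read and analysed.
2. In section 8.3, record from each patient's existing radiation plan the mean dose delivered by the second scan to each QCT region, and by surgery to the iliac and sacral biopsy sites.
3. In section 14, keep all patients in the primary paired analysis. Pre-specify two supporting analyses: change in density against delivered dose, and a summary by in-field versus out-of-field status, with that status defined before scans are read.
4. Use L1/L2 as a within-patient reference, and the iliac sample as an unirradiated control, only where the radiation plan confirms that they were outside the field.

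The cost is one dose look-up per patient and a little more analysis. There is no new scan or visit and no change in care. If coverage turns out to be complete, the trial will have documented its exposure, which is useful to the later studies this pilot is meant to inform.

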Cellular content of bone can be evaluated by immunohistochemical staining methods. Osteoblasts will be counted on toluidine blue stained slides as blue/grey cuboidal cells in clusters at the bone surface. Osteoclasts will be counted on slides assayed for TRAP activity as TRAP-positive multinucleated cells.

What is measured:

- Osteoblast number (N.Ob/BPm, mm^{-1})
- Osteoblast surface (Ob. S/BS, %)
- Osteoclast number (N.Oc/BPm, mm^{-1})
- Osteoclast surface (Oc.S/BS, %)

8.3.6 *Micro-CT*

Undecalcified biopsies will be scanned with a micro-CT system (X-Tek HMXST 225 microfocus X-ray system, Nikon Metrology, Tring, UK).

What is measured:

- Bone volume fraction (BV/TV)
- Trabecular thickness (Tb.Th.)
- Trabecular separation (Tb.Sp.)
- Trabecular number (Tb.N.)
- Connectivity density (Conn.D)
- Structure model index (SMI)
- Trabecular bone pattern factor (TBPf)

8.3.7 *Nanoindentation*

Experimental design, data collection and analysis for nanoindentation will be done by our collaborator [name], who has the expert knowledge and experience with this technology. Bone samples for nanoindentation cannot be embedded in paraffin because it would alter the elastic properties. The portion of the biopsy specimen for nanoindentation will be collected and stored in a small amount of normal saline solution at 4°C. Bone can remain stored in this fashion for several weeks without compromising the quality of the data. Measurements will be done with a nanoindentation tester (Agilent G200 Nanoindenter, Santa Clara, CA) equipped with a diamond tip of Berkovich. The indentation will be performed with a load of 5 mN.

What is measured:

- Elastic modulus

8.3.8 *Tetracycline Quadruple Labeling*

We will use a quadruple labeling schedule, using two sets of double tetracycline labels which differ in color under fluorescent light (ie tetracycline and demeclocycline). Figure 12 shows the schedule for the administration of the bone labeling drug. This way we will be able to distinguish the first and second label

[figure not shown]
CONFIDENTIAL
This document is confidential. Do not disclose or use except as authorized.

set. This technique has the great advantage that the patient can serve as his or her own pretreatment control, eliminating problems caused by the large intersite variability in histomorphometric variables

What is measured:

- Mineral apposition rate
- Mineral formation rate
- Mineralization lag time

Figure 12: Tetracycline Administration Schedule

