The Kolmogorov–Smirnov test on the normality of the distribution of bone mineral density and trabecular bone mineral density values will be carried out in each group. To evaluate the effects of radiation, we will

CONFIDENTIAL

This document is confidential. Do not disclose or use except as authorized.

use the Student t-test and Mann–Whitney test to compare the results from the iliac crest and the sacrum. We will use the Cox stratified model to identify confounding factors.

We plan to enroll 1-2 subjects per month. Subject enrollment is limited by patient availability.

The estimated study accrual by gender, race and ethnicity is shown in the table below.

Accrual Targets				
Ethnic Category	Sex/Gender			
	Females		Males	Total
Hispanic or Latino	1	+	0	= 1
Not Hispanic or Latino	14	+	15	= 29
Ethnic Category: Total of all subjects	15	+	15	= 30
Racial Category				
American Indian or Alaskan Native	0	+	0	= 0
Asian	0	+	0	= 0
Black or African American	1	+	1	= 2
Native Hawaiian or other Pacific Islander	0	+	0	= 0
White	14	+	14	= 28
Racial Category: Total of all subjects	15	+	15	= 30

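### Biopsies are coded only after analysis and no masked reading is specified, so the study code cannot mask readers to biopsy site in the iliac-versus-sacrum comparison

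*Combined protocol and SAP*

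**What the plan says.** Each patient in the surgical arm has two biopsies, with two bone samples collected at each (section 8.3.3). The roles are fixed in advance: "The first biopsy (the control) will be taken from the iliac wing of the pelvis", and "The second biopsy will be taken from the irradiated part of the sacrum". Biopsies go to an outside university laboratory in batches. The same paragraph then turns to coding: "After all studies have been performed we will label the biopsies with a code". It adds the code's purpose, "The key to the code will connect the biopsy with the subjects health information", says that the principal investigator holds the key, and moves on to storage.

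Section 8.3.5 defines the cell readings. The rule for bone-forming cells is "Osteoblasts will be counted on toluidine blue stained slides as blue/grey cuboidal cells in clusters at the bone surface". Bone-resorbing cells have a rule of their own, based on a different stain: "Osteoclasts will be counted on slides assayed for TRAP activity as TRAP-positive multinucleated cells". Section 2.4.3 derives the mineral apposition rate from the distance between the midpoints of two consecutive labels.

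Section 14.2 gives the analysis: to evaluate radiation effects, the investigators will "use the Student t-test and Mann–Whitney test to compare the results from the iliac crest and the sacrum".

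Section 14.1.2 lists these biopsy measurements as exploratory endpoints, while sections 1.3.2 to 1.3.4 present the biopsy work as secondary objectives. The primary endpoint in section 14.1.1 is the change in trabecular bone mineral density on QCT.

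**The concern.** The sacral-iliac contrast is the plan's direct tissue comparison of irradiated with non-irradiated bone. Part of it rests on human judgement: whether a cell is cuboidal and clustered at the surface, whether it is multinucleated and TRAP-positive, and where a label's midpoint lies. Section 2.4 states the expectation that irradiation degrades bone. With known site and a directional expectation, a reader's judgement can drift one way for sacrum and the other for ilium. That drift would enter the section 14.2 comparison and could not be told apart from a radiation effect.

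The plan already has a code, a key and a key-holder. As scheduled they cannot prevent this, because the code arrives after the readings. Section 14.2 says that the pilot is partly meant to supply numbers for later studies, so a distorted estimate would carry forward. Masking cannot be restored once a specimen has been read.

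**Working it through.** No figure in the plan bears directly on this point, so the main check sets the sections side by side.

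1. **Timing.** Section 8.3.3 places coding after all studies. A label applied after a reading cannot have masked it.
2. **Other masking.** No section says that readers of histology, micro-CT, nanoindentation or fluorescent labels are masked to site. None says that they are told the site either.
3. **What the code conceals.** As described, it links a biopsy to a subject's health information. Nothing says that it hides iliac or sacral origin. Moving it earlier unchanged would therefore not be enough; it must also conceal site.
4. **Which readings are exposed.** Exposure is clearest for osteoblast number and surface and osteoclast number and surface (section 8.3.5), and for label-based measurements compared between sites (section 8.3.8). It is weaker for elastic modulus, which is computed from the unloading curve (section 2.4.5), and for micro-CT parameters, which come from instrument output (section 8.3.6).
5. **What coding cannot mask.** The before-and-after contrast from quadruple labelling lies within one specimen and is identified by label colour by design.
6. **Primary endpoint.** QCT density does not come from biopsies and is not affected.

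**Illustration only.** The documents give no size for reader bias, so the shifts below are assumptions. Take n = 20 pairs (the planned surgical arm), a paired t-test at two-sided 0.05, no true difference between sites, and a systematic reading shift of b standard deviations of the paired difference. The rejection probability is

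P(|T| > t*), with T noncentral t on n − 1 = 19 degrees of freedom, noncentrality b√n, and t* = 2.093.

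As a check on the method, replacing b by the plan's own effect for the primary endpoint, 10/15, gives noncentrality 0.667 × √20 = 2.98 and probability 0.807. This is the power that section 14.2 states for 20 patients.

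| Assumed shift b | b√20 | Rejection probability |
|---|---|---|
| 0 | 0 | 0.050 |
| 0.1 | 0.447 | 0.071 |
| 0.25 | 1.118 | 0.186 |
| 0.5 | 2.236 | 0.5645 |

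Rounded, these are 5%, 7%, 19% and 56%. They show how the comparison would respond if such a shift existed. They are not evidence that one will occur.

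**The case against.** The strongest reply is that the late code is a confidentiality step before storage, not a blinding device, and that the plan is simply silent on what readers see. The laboratory may mask specimens by its own practice. This stands. A reader might infer from section 8.3.3 that the biopsies will be read unblinded, but the text shows only that the study code cannot provide masking and that none is specified.

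Section 8.3.1 has the same wording for blood: "After all studies have been performed we will label the samples with a code". It is tempting to extend the point to serum. The documents do not support that. Blood is drawn serially from each patient, there is no irradiated and control pair, and the listed markers are laboratory concentrations with no subjective reading step described.

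A third reply is that earlier coding is not free and could clash with the workflow. This also stands in part. Under section 8.3.3 the preferred sacral sample is taken from the resected specimen after it reaches surgical pathology, so it cannot be coded on leaving the operating room. Section 8.3.4 requires one control and one experimental sample to be chosen for embedding, which needs the site to be known at that step. Coding therefore has to follow sampling and allocation.

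Finally, the illustration assumes a paired test and identical bones. Section 14.2 names the Student t-test and Mann–Whitney test without saying that the analysis is paired. Sections 2.4.3 and 8.3.8 themselves warn of large variability between sites. A true iliac-sacral difference unrelated to radiation may exist, and masking does not remove it. This limits the use of the percentages, but not the case for masking.

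**Conclusion.** The point holds for the biopsies. Coding follows all analysis, no masked reading is described, and the iliac-versus-sacrum comparison includes observer-dependent counts and label measurements. The study code as scheduled cannot protect that comparison from reader bias.

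The size of any bias is unknown. The 7%, 19% and 56% rates rest entirely on assumed shifts of 0.1, 0.25 and 0.5 SD and should not be cited as an estimate of harm. The consequence is confined to exploratory endpoints of a pilot; the primary endpoint, sample size and stated power do not change. It still merits correction before specimens are read, because the remedy is small and cannot be applied afterwards.

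The documents do not support going further: that readers certainly know the site, that serum results share the problem, or that the change would cost nothing.

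**What to change.** In section 8.3.3, replace the sentence on coding after all studies with a rule to this effect: once the biopsy samples have been obtained and allocated to each technique, and before they are shipped to the analysing laboratories, each sample receives a code that conceals both patient and site (iliac or sacral). The principal investigator keeps the key and opens it only after the readings are locked. Add one sentence saying which readers are masked and to what. Section 8.3.1 need not change on this ground.

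The cost is slightly earlier labelling work and a revised paragraph. Masking will be partial: a reader may recognize the site from morphology, and the two label sets remain distinguishable by colour within a specimen. The report should state both limits.
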